13.1.5 Summary by Visit

Summary statistics of ML score (continuous variable) and change from baseline at each windowed visit will be produced. A tabulation of ML score (categorical variable) and change from baseline at Weeks 48, 96, 144, and last assessment will also be provided.

For comparison with Study 190-901, to enable a descriptive assessment of ML scores at common time points where all subjects contribute to the descriptive statistics, each subject of the matching cohorts will have their ML scores imputed to those time points using linear interpolation. The time points for interpolation will be in accord with the Study 190-203 schedule of CLN2 assessments. [Appendix 4](#) describes the imputation procedure in greater detail. Summary statistics

	BMN 190-203 Statistical Analysis Plan, Version 2.0	Pg. 29 of 53
---	---	--------------

of interpolated values and change from baseline by visit will be produced for the matched groups. A graph of mean change from baseline and standard error by visit will be produced.

13.1.6 Subscales M and L

The rate of decline, time-to-event (unreversed 2-point decline or score of zero, unreversed 1-point decline), summary by time point, and categorical change from baseline analyses will be performed for the separate M and L scales. Patients with baseline M=0 (or L=0) will be excluded from the M (or L) rate of decline and time-to-event analyses.

13.1.7 Comparisons with Siblings

If natural history data are available on siblings with disease, ML, M, and L scales of sibling pairs may be graphed.

13.2 Secondary Efficacy Endpoint(s)

13.2.1 Time to Disease Manifestation

For analysis purposes, asymptomatic patients are defined as the patients with baseline MLVS = 12. Subsequent disease manifestation is defined as post-baseline consecutive measurements of M, L, V, or S scores that are less than 3 and at least 22 days apart. The time of disease manifestation is defined as the time of the first of the two measurements demonstrating the deficit. Kaplan-Meir analysis will be performed.

For patients who have not presented with CLN2 disease symptoms prior to initiation of treatment (baseline), onset of disease symptoms captured in AE reporting will be described.

13.2.2 MLV and MLVS

The MLV and MLVS scores will be summarized and interpolated similarly to the ML endpoint (Section 13.1.5). The categorical variable summaries will not be produced.

13.2.3 MRI parameters

Brain atrophy will be evaluated with one or more of the following MRI measurements:

- Whole brain volume (WBV) (in mm³)
- Volume of cerebrospinal fluid (in mm³ and as a percentage of WBV)
- Volume of cortical gray matter (in mm³ and as a percentage of WBV)
- White matter volume (in mm³ and as a percentage of WBV)

BIOMARIN®	BMN 190-203 Statistical Analysis Plan, Version 2.0	Pg. 30 of 53
------------------	---	--------------

- Whole brain apparent diffusion coefficient (mm²/s)
- Results will be summarized descriptively over time.

Comparisons with natural history may be produced if MRI data are available. If natural history data are available on siblings with disease, MRI parameters of sibling pairs may be graphed.

Draft

	BMN 190-203 Statistical Analysis Plan, Version 2.0	Pg. 31 of 53
---	---	--------------

13.3 Exploratory Endpoints

13.3.1 PedsQL

The PedsQL™ Generic Core Scales are designed to measure Quality of Life in children and adolescents. The assessments are brief, practical and developmentally appropriate. It will be performed at Baseline visit prior to first infusion, every 12 weeks till study completion / early termination.

13.3.1.1 PedsQL - Parent Report

The four parent reports cover the ages from 1-12 months, 13-24 months, 2-4 years (toddlers) and 5-7 years (young child). It includes questions regarding physical, emotional, and social functioning, with school functioning where applicable.

This will be summarized as described in the PedsQL documentation, “Scaling and scoring of the Pediatric Quality of Life Inventory PedsQL.” The following text briefly summarizes the scoring of the Parent Report:

The Parent Report for various ages is composed of 21 (or 23 items) comprising 4 dimensions:

- Physical Functioning (8 items)
- Emotional Functioning (5 items)
- Social Functioning (5 items)
- School Functioning (5 items for young child or 3 items for toddlers)
- Each item is scored on a 5-point Likert scale from 0 (Never) to 4 (Almost always).

The scoring procedure is as follows: Items are reverse-scored and transformed to a 0-100 scale as follows: 0=100, 1=75, 2=50, 3=25, 4=0.

Score by dimension: If more than 50% of the items in the scale are missing, the scale scores should not be computed. The mean score = Sum of the items over the numbers of items answered.

Psychosocial Health Summary Score: This is the sum of the items over the number of items answered in the Emotional, Social, and School Functioning scales.

Total Score: This is the sum of all the items over the number of items answered on all the scales.

The various scores (by dimension, psychosocial health summary, and total scores) will be provided in a listing.

	BMN 190-203 Statistical Analysis Plan, Version 2.0	Pg. 32 of 53
---	---	--------------

13.3.1.2 PedsQL - Parent Family Impact

This will be summarized as described in the PedsQL documentation, “Scaling and scoring of the Pediatric Quality of Life Inventory PedsQL.” The following text briefly summarizes the scoring of the Parent Family Impact:

The full PedsQL Family Impact Module is composed of 36 items comprising 8 dimensions:

- Physical Functioning (6 items)
- Emotional Functioning (5 items)
- Social Functioning (4 items)
- Cognitive Functioning (5 items)
- Communication (3 items)
- Daily Activities (3 items)
- Family Relationships (5 items)
- Worry (5 items)

Each item is scored on a 5-point Likert scale from 0 (Never) to 4 (Almost always).

The scoring procedure is as follows: Items are reverse-scored and transformed to a 0-100 scale as follows: 0=100, 1=75, 2=50, 3=25, 4=0.

Score by dimension: If more than 50% of the items in the scale are missing, the scale scores should not be computed. The mean score = Sum of the items over the numbers of items answered.

Parent HRQL Summary score (20 items): This is the sum of the items over the number of items answered in the Physical, Emotional, Social, and Cognitive scales.

Total Score: This is the sum of all the items over the number of items answered on all the scales.

The various scores (by dimension, parent HRQL, and the total scores) will be provided in a listing.

	BMN 190-203 Statistical Analysis Plan, Version 2.0	Pg. 33 of 53
---	---	--------------

13.3.1.3 PedsQL – Young Child (5-7 years) Self-reported

The young child ages (5-7 years) self-reported is composed of 23 items comprising 4 dimensions:

- Physical Functioning (8 items)
- Emotional Functioning (5 items)
- Social Functioning (5 items)
- School Functioning (5 items)
- Each item is scored on a 3-point scale: 0 (Not at all), 2 (Sometimes) and 4 (A lot) for the ages 5-7 years child report.

Young child self-report has been removed from the eCRF from 22 October 2018. Data collected in database will be provided in a listing.

13.3.2 CLN2-specific Quality of Life Questionnaire

The CLN2-specific QoL Questionnaire is a disease specific supplement to the PedsQL using the same format and quantitation. It will be performed at Screening, at the Baseline visit prior to first infusion, and every 12 weeks until study completion / early termination.

This instrument was developed by BioMarin, modeled upon the PedsQL instruments, and will be summarized similarly to the PedsQL instruments, as described below.

The CLN2 -specific QOL instrument is composed of 28 items comprising 6 dimensions:

- Seizures (6 items)
- Feeding / No G-tube (4 items)
- Feeding / with G-tube (3 items)
- Sleep (5 items)
- Behavior (6 items)
- Daily activities (4 items)
- Each item is scored on a 5-point Likert scale from 0 (Never) to 4 (Almost always).

The scoring procedure is as follows: Items are reverse-scored and transformed to a 0-100 scale as follows: 0=100, 1=75, 2=50, 3=25, 4=0.

Score by dimension: If more than 50% of the items in the scale are missing, the scale scores should not be computed. The mean score = Sum of the items over the numbers of items answered.

	BMN 190-203 Statistical Analysis Plan, Version 2.0	Pg. 34 of 53
---	---	--------------

Total Score: This is the sum of all the items over the number of items answered on all the scales. The scores (by dimension, and total) and change from baseline will be provided in a listing.

13.3.3 Denver II Developmental scale

The Denver II is a revision and update of the Denver Developmental Screening Test. Both tests were designed to monitor the development of infants and preschool-aged children. The tests cover four general functions: personal social (such as smiling), fine motor adaptive (such as grasping and drawing), language (such as combining words), and gross motor (such as walking). It includes the number of passes, number of fails, number of cautions, number of delays and developmental age of most advanced pass. Overall test interpretation is provided as well.

The overall interpretation of the test – normal, suspect, or untestable – will be summarized by visit.

Age equivalent performance, number of passes, and number of fails on personal social, fine motor adaptive, language and gross motor will be plotted over time using the age at assessment for each subject. Age equivalence and change from baseline will be summarized. The ratio of change in age equivalence and change in age will be summarized at each visit as well as the last visit.

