Blood/urine for clinical lab tests ^q		X	D2	Q4W x 2 (Wks 1-9), then Q8W x 5 (Wks 17-49), then Q12W (Wks 61-145)	Х	X	X
Modified Unified Batten Disease Rating Scale Involuntary Movement Scale		X		Q12W			
Modified Unified Batten Disease Rating Scale Seizure Inventory		Х		Q12W			
Optical coherence tomography ^r		X		Q24W	Х		

	Screening ^a	Baseli	ine/First Infusion	Treatment Period Weeks 1 to 144	Study Completion / Early Termination	Device Safety Follow-Up	Safety Follow-Up
Assessments and Events	≤ 21 days prior to ICV Surgery	≤2 Days prior to first dose	First Infusion Visit (Days 1-6)	Visit every 2 weeks (±3 days)	Proximity to last dose (+3 days)	4 weeks after device removal (±3 days)	6 months after last dose ±1week
PedsQL ^s		Х		Q12W	Х		
Denver II Developmental Scale ^t		Х		Q12W	Х		
CLN2-specific QoL questionnaires	Х	Х		Q12W	Х		
Ophthalmologic assessments		Х		Q48W	Х		
Visual acuity testing ^u		Х		Q12W	Х		
Pregnancy testing (in females of childbearing potential) ^v	Х				Х		
Adverse events, including ongoing seizure history ^w	Х			Continuous monito	oring		
Prior and concomitant medications, including anti- epileptic treatments ^x	Х			Continuous monito	oring		
Hypersensitivity Labs ^y		As neede	d, only in the event of susp	pected anaphylactic r	eaction, serious or	severe hyperse	nsitivity ^y
ICV Device Removal ^z					Xz		

Baseline values will be recorded no more than two days before the first infusion, which will occur at least 14 days from surgery and no more than 28 days after surgery. Thereafter, study visits will be every 2 weeks ± 3 days from the date of the first infusion. If a subject is discontinued from the study prematurely, an Early Termination visit should be scheduled within 3 days.

^a Written informed consent must be obtained before study procedures begin. All screening procedures are to be completed ≤21 days prior to the ICV implant surgery. Sponsor approval must be obtained prior to ICV implant surgery.

^b Diagnosis of CLN2 disease determined by TPP1 enzyme activity (dried blood spot) in the fibroblasts and leukocytes available at Screening. In addition, blood for TPP1 enzyme activity and CLN2 gene analysis will be collected to be analyzed centrally.

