9.3.1 Inclusion Criteria

• Diagnosis of CLN2 disease as determined by TPP1 enzyme activity (dried blood spot) in the fibroblasts and leukocytes available at Screening. *Note: Blood for TPP1 enzyme activity and CLN2 gene analysis must be collected to be analyzed centrally.*

- Quantitative clinical assessment of the Hamburg motor-language aggregate score 3-6 at Screening, as defined in the Ratings Assessment Guideline.
- < 18 years of age at the time of informed consent
- Written informed consent from parent or legal guardian and assent from subject, if appropriate
- Males and females who are of reproductive age should practice true abstinence, defined as no sexual activity, during the study and for 6 months after the study has been completed (or withdrawal from the study). If sexually active and not practicing true abstinence, males and females of reproductive age must use a highly effective method of contraception while participating in the study.
- Ability to comply with protocol required assessments (ICV implantation, drug administration, laboratory sample collection, EEG, ECG, MRI, etc.)

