9.7.1.3 Denver Development Scale II

The Denver II is a revision and update of the Denver Developmental Screening Test. Both tests were designed to monitor the development of infants and preschool-aged children. The tests cover four general functions: personal social (such as smiling), fine motor adaptive (such as grasping and drawing), language (such as combining words), and gross motor (such as walking). Ages covered by the tests range from birth to 6 years.

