9.7.1.6 PedsQL

The PedsQLTM Generic Core Scales are designed to measure Quality of Life in children and adolescents. The assessments are brief, practical and developmentally appropriate. The instrument is responsive to clinical change over time (Msall, 2005). The four parent reports cover the ages from 1-12 months, 13-24 months, 2-4 years, and \geq 5 years, and include questions regarding physical, emotional, and social functioning, with school functioning where applicable. Patients who become older than age 5 during the study will no longer be assessed using this tool.

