3.4 Study Dosage and Administration

BMN 190 is administered every 14 days from the date of the first infusion (± 3 days) for at least 144 weeks according to the subject's age:

- birth to < 6 months: 100 mg
- 6 months to < 1 year: 150 mg
- 1 year to < 2 years: 200 mg (first 4 doses), 300 mg (subsequent doses)
- ≥ 2 years: 300 mg

	BMN 190-203 Statistical Analysis Plan, Version 2.0	Pg. 13 of 53
---	---	--------------

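### SAP 13.3.3 sets no age or ceiling rule for the Denver II age-equivalence ratio, so a child who reaches the top of the test shows a ratio below 1 even with normal development

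*SAP*

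**What the plan says.** SAP 13.3.3 summarizes the Denver II overall interpretation (normal, suspect or untestable) by visit. It also summarizes age equivalence and its change from baseline, and then a ratio: "The ratio of change in age equivalence and change in age will be summarized at each visit as well as the last visit". One recorded quantity is the "developmental age of most advanced pass". The section describes the target population only in general terms: "Both tests were designed to monitor the development of infants and preschool-aged children".

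The numeric range is in Protocol 9.7.1.3: "Ages covered by the tests range from birth to 6 years". The June 2020 SAP repeated that range in its section 12.3.3; version 2.0 does not carry it.

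Nothing else in the documents keeps assessments inside that range:

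- Entry (Protocol 9.3.1): "< 18 years of age at the time of informed consent".
- Schedule (Protocol Table 9.1.1, 12.7 and 12.10): Denver II at baseline, every 12 weeks, and at completion or early termination, with no age at which it stops.
- Windows (SAP Appendix 1): the last Denver II window is Week 145 and takes every assessment from Day 968 on.
- Population (SAP 13): efficacy analyses use the ITT population, with no age restriction for this instrument.

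For PedsQL the protocol does write an age stop (9.7.1.6): "Patients who become older than age 5 during the study will no longer be assessed using this tool". Denver II has no parallel sentence.

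**The concern.** The ratio reads as a rate of development: 1 means a month of development gained per month of age, and less than 1 means delay. That reading fails once a child has reached the highest age equivalent the test can give. From then on the change in age equivalence is fixed while the change in age keeps increasing, so the ratio falls although nothing has happened to the child. A child already at the top at baseline shows 0 throughout.

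The last-visit summary is the most exposed, because it takes each child at the oldest age. The children at risk are the older, best-preserved ones, so the artefact understates development where function was kept. In a table of means it cannot be told apart from true delay.

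The overall interpretation has a related problem. The plan tabulates it at every visit, including visits made when the child is older than the ages the test covers, and does not say what a rating means there.

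Developmental achievement is a stated exploratory objective (SAP 3.1), and the Denver II is the developmental instrument the SAP analyses for it.

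**Working it through.** The plan states no value for this ratio, so there is no figure to reproduce. The check is what the rule returns for a child developing normally.

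**Inputs**

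- Upper age of the test: 6 years (Protocol 9.7.1.3).
- Follow-up: 144 weeks from first dose (Protocol 9.1; SAP 3.4).
- Ceiling C on the age equivalent: not in the documents. I take C = 6 years (72 months) from the age range, and vary it from 5.5 to 6.5 years. That a ceiling exists is my reading of an age equivalent based on the most advanced item passed.

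**Step 1. Who passes age 6 on study.** 144 × 7 / 365.25 = 2.76 years = 33.1 months. 6 − 2.76 = 3.24 years. A child older than 3.24 years at first dose is past age 6 at Week 145.

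**Step 2. The ratio for a normally developing child.** With baseline age b, time since baseline t, and age equivalent equal to age up to C:

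ratio(t) = [min(b + t, C) − min(b, C)] / t

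With C = 6 years, and t = 48, 96 and 144 weeks (0.92, 1.84 and 2.76 years):

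| Baseline age (years) | 48 weeks | 96 weeks | 144 weeks |
|---|---|---|---|
| 3.0 | 1.00 | 1.00 | 1.00 |
| 3.5 | 1.00 | 1.00 | 0.91 |
| 4.0 | 1.00 | 1.00 | 0.72 |
| 4.5 | 1.00 | 0.82 | 0.54 |
| 5.0 | 1.00 | 0.54 | 0.36 |
| 5.5 | 0.54 | 0.27 | 0.18 |
| 6.0 or over | 0 | 0 | 0 |

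For example, at 4 years: (72 − 48) / 33.1 = 0.72. The true value is 1 in every cell.

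**Step 3. Sensitivity to the ceiling.** For the same 4-year-old at 144 weeks:

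- C = 5.5 years: (66 − 48) / 33.1 = 0.54; the baseline-age threshold becomes 2.74 years.
- C = 6.5 years: (78 − 48) / 33.1 = 0.91; the threshold becomes 3.74 years.

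The fall appears at each ceiling tried; only its onset moves.

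**Step 4. Who is not affected.** What binds is the age equivalent, not chronological age. With C = 72 months, a child whose baseline age equivalent is at most 72 − 33.1 = 38.9 months, gaining at or below the normal rate, cannot reach the ceiling by Week 145 at any age.

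- Aged 4 with an age equivalent of 36 months, gaining at the full rate: 36 + 33.1 = 69.1 months, ratio 1.00.
- Age equivalent at half of age, enrolled at 4, 5 or 6 years: ratio 0.50, as it should be.
- Age equivalent at three quarters of age: 0.75 if enrolled at 4 or 5 years, but (6 − 4.5) / 2.76 = 0.54 instead of 0.75 if enrolled at 6. So the ceiling can also bind in an older child with mild delay.
- Under 2 years at first dose: younger than 2 + 2.76 = 4.76 years at Week 145, so inside the range throughout.

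**The case against.** The strongest reply is that few children may be affected. Protocol 7 puts symptom onset typically at 2 to 4 years, with impaired speech and developmental regression following, and the enrolment plan calls for at least 5 children with a motor-language score below 5. Many children older than 3.24 years may therefore have an age equivalent well below the ceiling. SAP Appendix 3 speaks of potentially 14 matched pairs. If that is the treated number and the quota of at least 5 children under 2 was met, at most 14 − 5 = 9 could be older than 3.24 years, and how many of those are near normal is unknown. All of this stands.

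It also stands that the documents give no scoring table, so 72 months is inferred, and that SAP 13.3.3 plots each child's age equivalent, passes and fails against age, where a plateau could be seen. The plots do not repair the tabulated ratio, which a reader of the report will take at face value.

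Three stronger readings are tempting and are not supported:

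- That the ratio is wrong for every child past age 6. Step 4 of the working shows otherwise.
- That the artefact could manufacture a benefit. It lowers the ratio, and the matched natural-history comparisons in SAP 13 cover the CLN2 scales, not Denver II.
- That every assessment after 72 months should leave the summaries. An older child whose age equivalent drops from 30 to 12 months is nowhere near the ceiling. Removing that child would hide real late regression and could flatter treatment.

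**Conclusion.** The concern holds in a limited form. Followed as written, SAP 13.3.3 gives a ratio below 1 to a normally developing child whose age equivalent reaches the top of the test, and tabulates the overall interpretation at ages the protocol says the test does not cover. For a normally developing child enrolled at 4 years, the highest Week 145 ratio is 0.72 under an assumed 72-month ceiling, with a range of 0.54 to 0.91 for ceilings of 5.5 to 6.5 years.

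This rests on two assumptions: testing continues after age 6, which the schedule implies, and the age equivalent stops at the top of the test. The documents do not say how sites score a child over 6. Enrolled ages are not given, so neither the number of children affected nor the shift in any group mean can be computed. With about 14 children, though, a single capped child could move a mean visibly. The endpoint is exploratory and descriptive, and the primary analysis is untouched. It should be corrected, but it is not critical.

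**What to change.** In SAP 13.3.3:

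1. Report the ratio, and the last-visit ratio, for assessments made at or before 72 months of age, with the last visit taken as the last such assessment. Place this beside the all-assessment summary, which stays so that late regression in older children remains visible.
2. Flag and count scores at the top of the scale at each visit, and state what that top score is. This also covers the case where the true ceiling lies below 72 months.
3. Tabulate the normal/suspect/untestable interpretation only for assessments within the instrument's age range, and list the rest.
4. Show the number of children in range at each visit.

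Under a 72-month ceiling, a normally developing child then keeps a ratio of 1.00 at every in-range visit, and a child aged 6 or over at baseline contributes no in-range ratio.

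The cost is a paragraph of SAP text and a filter on age in months, which SAP 4.6 says is provided at each Denver assessment. The downsides are a few more table columns and a smaller N in the in-range summary at late visits. No new data are needed and none are lost.

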13.3.4 Modified Unified Batten Disease Rating Scale Involuntary Movement Scale (mUBDRS-Movement)

The modified Unified Batten Disease Rating Scale Involuntary Movement (mUBDRS-Movement) inventory is a rating scale that measures the type, frequency and severity of 5 common involuntary movements (7 items) associated with CLN2 disease:

- Myoclonus (maximal) (2 items: frequency and severity)
- Dystonia (maximal) (2 items: frequency and severity)
- Dysmetria
- Chorea
- Tics/Stereotypy

Each item of the frequencies of Myoclonus and Dystonia is scored on a 4-point Likert scale: 0=“Not present during exam” or “Absent during exam”, 1=“Present, but rarely occurs”, 2=“Periods of activity with pauses” and 3=“Occurs regularly”.

BIOMARIN®	BMN 190-203 Statistical Analysis Plan, Version 2.0	Pg. 35 of 53
------------------	---	--------------

Each item of the severities of Myoclonus and Dystonia is scored on a 4-point Likert scale: 0=“Not present during exam” or “Absent during exam”, 1=“No impairment of activity”, 2=“Some impairment of activity” and 3=“Often impairment of activity”.

The item of Dysmetria is scored on a 4-point Likert scale: 0=“Normal finger-to-nose or reach to object”, 1=“Accurate, mild loss direction/velocity”, 2=“Occasional miss of target” and 3=“Unable to touch/reach target”.

Each item of Chorea and Tics/stereotypy is scored on a 4-point Likert scale: 0=“Absent during exam”, 1=“Slight and intermittent”, 2=“Mild/moderate and intermittent” and 3=“Pronounced and common”.

Total Score: This is the sum of all the items over the number of items answered on all the scales. If more than 50% of the items in the items are missing, the total scores should not be computed. Total score and change from baseline will be provided in a listing.

